8.7. Response Determination

The month 1 post-ablation CT examination will be used as the reference for determining index ablation zone response at each follow up interval after cryoablation. Sequential follow up intervals will be used to determine local failure.

In the unforeseen circumstance where the patient is unable to complete imaging according to the month 1 follow up visit, the month 3 imaging study may serve as the reference for determining index tumor response at each follow up interval after cryoablation. Every effort should be made to comply with the month 1 imaging requirement.

Efficacy at 12 months post cryoablation will be based on local tumor control that will be separately assessed for each index tumor according to criteria below. Each ablation zone will be evaluated at each time point by measuring its 3 axes (longest diameter and the two perpendicular diameters). For each ablation zone individually, the sum of these three measures will be compared to the 1 month baseline for tumor response and the previous follow up interval imaging study for local failure.

Each ablation zone measurement assessment, along with the overall clinical evaluation of the patient, will be evaluated by an independent imaging panel to assess the final response determinations. This final review can be used in the analysis in the event of 'indeterminate' imaging measurement assessments.

Local Tumor Control will be defined as the absence of local failure.

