7.5. Month 1 – Follow-up

Patients will return 1 month (30 days $-7/+21$) post cryoablation procedure. In the event of multiple cryoablation procedure dates, the most recent procedure date will serve as the reference for determining the follow up visit window.

The following assessments will be completed:

- Quality of Life assessment (SF-12);
- Karnofsky Performance Scale;
- Safety assessment;
- Chest CT scan \pm contrast (contrast is preferred) to identify possible post-procedure adverse events. This 1 month imaging will serve as the new baseline for tumor response evaluation;
- Assessment of metastatic lung disease progression beyond the index tumor(s) and feasibility of treatment;
- Assessment of local tumor recurrence at the index tumor, including additional treatment and feasibility of treatment;
- Assessment of any systemic cancer treatment(s);
- Assessment of any local therapy for the index tumor(s).
- Current pertinent concomitant medication.

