8.7.4 Local Failure

Local failure will be defined as $\geq 20\%$ increase in the sum of the three axes of measurements (longest diameter plus the two perpendicular diameters) when compared with the nadir of this 3 axes measurement.

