10.3. Analysis Populations

All primary efficacy analyses will be performed on all treated tumors with a Galil Medical Cryoablation System and needles as intent-to-treat population. A supplemental per-protocol analysis will be done for the primary efficacy endpoint, removing index tumor which did not have a complete treatment and/or those that did not meet the study criteria but were enrolled.

The intent-to-treat and per-protocol analyses will be compared for level of agreement. It is expected that the two tumor populations will be similar; however, any substantial differences between the two will be analyzed appropriately to elucidate the cause of these differences.

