10.5.5. Other Data Assessments

Technically successful treatment definition

A technically successful treatment will be defined by the presence of an ablation zone, ground glass opacity, or frank consolidation encompassing the targeted index tumor(s) no later than the 1 month follow up visit after the cryoablation procedure. Technical success will be analyzed on a per tumor basis.

Disease recurrence or progression definitions

The reference date for disease progression evaluation will be associated with the initial (first) cryoablation procedure done per study protocol. In the event of multiple cryoablation procedure dates, such as with bilateral lesions or staged treatments, the date of reference for disease progression evaluation will be the initial (first of n) cryoablation procedure.

- **Local disease progression** will be determined locally by evidence of local tumor failure.
- **Lung-disease-specific survival rate** is defined as the time in days from the first cryoablation procedure to death and **a)** the date of metastatic lung tumor progression (new lung tumors or local tumor failure of the index tumor), **b)** the date of death with local control of the index tumor, or **c)** the date of last follow up in patients who were still alive with local tumor control of the index tumor. Patients who are alive will be censored at the date of their last visit. Patients who have died from causes other than local failure of the index tumor will be censored at the time of death. Lung disease-specific survival rates will be summarized by using Kaplan-Meier methodology.
- **Overall survival rate** is defined as the time in days from the first cryoablation procedure to death. Patients who are alive will be censored at the date of the last visit. Overall survival rates will be summarized by using Kaplan-Meier methodology.
- **Time to metastatic lung disease progression beyond the index tumor** is defined as the time in days from the first cryoablation procedure to metastatic disease beyond the index tumor site. Patients without metastatic lung disease progression will be censored at the date of their last visit or their date of death (due to any cause). Metastatic progression free survival rates will be summarized by using Kaplan-Meier methodology.

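### An index tumour that month-1 imaging shows was not covered by the ablation zone can still count as locally controlled, and no planned analysis scores it as a failure

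*Protocol*

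**What the plan says.** Protocol 7.5 resets the baseline after treatment: "This 1 month imaging will serve as the new baseline for tumor response evaluation". Section 8.7 repeats this for the ablation zone ("The month 1 post-ablation CT examination will be used as the reference for determining index ablation zone response") and allows a fallback if month-1 imaging is missed: "the month 3 imaging study may serve as the reference for determining index tumor response at each follow up interval after cryoablation".

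Section 8.7.4 gives one criterion for local failure, at least a 20% "increase in the sum of the three axes of measurements (longest diameter plus the two perpendicular diameters) when compared with the nadir". Section 8.7 names a different comparator, "the previous follow up interval imaging study for local failure". The endpoint then follows: "Local Tumor Control will be defined as the absence of local failure".

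Coverage of the tumour is defined elsewhere. Protocol 10.5.5 counts a treatment as technically successful if imaging shows an ablation zone, ground glass opacity or "frank consolidation encompassing the targeted index tumor(s) no later than the 1 month follow up visit". This is summarised per tumour among the other data, and the SAP lists it as a supportive endpoint. Neither document connects it to local control.

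The primary analysis takes all treated tumours (protocol 10.3; SAP, Analysis Populations). The supplemental per-protocol analysis works by "removing index tumor which did not have a complete treatment". The sensitivity analyses listed in the SAP under Handling of Missing Data (worst case, best case, complete case) concern only missing month-12 evaluations.

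**The concern.** The month-1 scan does two jobs that the plan does not link. It shows whether the ablation zone encloses the tumour, and it supplies the reference from which later growth is judged. A tumour found at month 1 to lie partly outside the zone is a technical failure, yet it enters follow-up with no local failure recorded. If the measured sum then stays below the threshold, it is a success in the primary analysis. In the per-protocol analysis it is at most removed. It is scored as a failure in neither.

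The trial is meant to show that cryoablation achieves local control, by comparing one rate with a fixed goal of 84%. With no control arm, there is nothing against which a lenient scoring rule would cancel out. The planned margin is also thin, so a few tumours credited this way could decide whether the goal is met.

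**Working it through.** **Inputs.** From protocol 10.1 and the SAP's Sample Size Justification: goal 84%, planned rate 91%, 203 evaluable tumours, goal met with 181 or more successes, tumours treated as independent, 10% attrition. Failure threshold of 20%: protocol 8.7.4. Visit windows: protocol Table 1. The share of uncovered tumours is not given; t below is an assumption, shown over a range.

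**The plan's own figures.** With X binomial (203, p):
- P(X ≥ 181 | p = 0.84) = 0.0239, as stated.
- P(X ≥ 181 | p = 0.91) = 0.8501, as stated.
- 203 / 0.90 = 225.6, rounded up to 226, as stated.

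**Margin.** Expected successes at 91% are 0.91 × 203 = 184.7, against a threshold of 181. The margin is 3.7 tumours. About four tumours (4/203 = 2%) use it up.

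**Chance of meeting the goal when true control is exactly 84%.** If a share t of tumours is uncovered but scored as controlled, the counted rate is 0.84 + t. If only half of them stay under the growth threshold, it is 0.84 + t/2.

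| t | All scored as controlled | Half scored as controlled |
|---|---|---|
| 0 | 2.4% | 2.4% |
| 1% | 5.5% | 3.7% |
| 2% | 11% | 5.5% |
| 3% | 21% | 8.0% |
| 5% | 53% | 16% |

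**The same question from the planned rate.** Suppose the 91% includes a share t of uncovered tumours. Rescoring all of them as failures gives P(X ≥ 181 | p = 0.91 − t): 70% at t = 1%, 53% at 2%, 35% at 3% and 11% at 5%, against 85% at t = 0.

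**What the growth threshold allows.** Equal growth of 20% on three axes multiplies volume by 1.2³ = 1.73, or log2(1.728) = 0.789 doublings. Over a nominal 335 days from month 1 to month 12, that is reached only if the volume doubling time is below 335 / 0.789 = about 425 days. The windows (month 1 at day 23 to 51, month 12 ± 30 days) make the interval 284 to 372 days and the cut-off about 360 to 471 days.

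The rise needed depends on the nadir. For a zone with a 90 mm sum at month 1 it is 18 mm with no shrinkage. It is 0.20 × 63 = 12.6 mm at the partial-response boundary (30% decrease) and 0.20 × 22.5 = 4.5 mm at the complete-response boundary (75% decrease). These are illustrations only: the protocol measures the ablation zone, not the residual tumour alone, and gives no growth rates.

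**The case against.** A reader might infer that every missed tumour ends as a success, or that the bias always runs one way. The documents do not support that. Under protocol 7.8 a retreated tumour restarts its follow-up. Other local therapy to an index tumour leads to withdrawal, and the missing month-12 status is then multiply imputed under the SAP unless failure was already seen at month 6. Section 7.10 discontinues patients whose supplemental treatment may affect the primary outcome, which limits any argument that systemic therapy holds residual tumour stable. The nadir comparator also makes failure easier to reach once the zone has shrunk.

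There are safeguards. An independent panel reviews measurements together with the clinical evaluation (8.7), a central reader adjudicates images (16.2), and follow-up visits from month 1 onward include a separate assessment of recurrence at the index tumour. These are only partial. The panel's use in the analysis is stated for indeterminate measurements, which a stable measurement is not, and no section gives a residual-tumour criterion for local failure.

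A post-ablation reference is reasonable, because the zone is meant to exceed the tumour, and technical success will be reported for readers to see.

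A reader might also conclude that the primary endpoint must be redefined. That goes too far. The documents do not say how the six series behind the 84% goal defined local control, so adding technical failure could correct the comparison or distort it. Technical success is also timed differently in the two documents, so a direct rule could fail covered tumours that were merely scanned late.

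**Conclusion.** The gap is real and tends to favour success. An index tumour shown at month 1 not to be covered counts as controlled in the primary analysis if it stays below the 20% threshold at month 12 and is not retreated or withdrawn. No planned analysis tests what happens if it is scored as a failure.

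The size cannot be fixed from the documents, because the technical failure rate is not stated. The probabilities above assume independent tumours, true control of exactly 84% and the sample-size decision rule. The SAP's actual test uses a random-effects logistic model with a Wald bound and multiple imputation, so they indicate order of magnitude and are not the trial's error rate. If technical failures prove very rare, the effect is small. At about 2% it is comparable to the whole expected margin.

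This supports a pre-specified sensitivity analysis. It does not by itself show that the primary result would be wrong.

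**What to change.** Add to the SAP a named sensitivity analysis of the primary endpoint. Every index tumour whose imaging shows it was not encompassed by the ablation zone is scored as a local failure from month 1. All other tumours are scored as now. Use the same random-effects model and multiple imputation, and report whether the lower 97.5% bound also exceeds 84%. Report the number of tumours reclassified. Do not apply the rule to tumours whose month-1 scan is only late or missing.

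Three texts need to be settled first:
- The timing of technical success. The protocol runs to the month-1 visit, whose window extends to day 51, while the SAP allows 30 days.
- The comparator for local failure. Section 8.7 uses the preceding scan and 8.7.4 uses the nadir.
- The SAP's pointer for the definition of tumour control. It cites Section 9.7, which the protocol does not contain; the criteria are in 8.7.

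The cost is one extra analysis on technical-success data already planned per tumour, with no new visits or imaging. The downside is a possibly less favourable supportive rate.

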8.7.1 Complete Response

Tumor/ablation zone disappearance or $\geq 75\%$ decrease in the 1 month baseline sum of the three axes of measurements (longest diameter and the two perpendicular diameters).

Note: If it is the opinion of the investigator that the tumor/ablation zone has likely disappeared, the measurement should be recorded as 0mm. If the tumor/ablation zone is believed to be present and is faintly seen but too small to measure, a default value of 1 mm will be assigned.

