8.7.3 Stable Disease

Stable disease will be defined as $< 30\%$ decrease in the 1 month baseline sum of the three axes of measurements (longest diameter and the two perpendicular diameters), and $< 20\%$ increase of the nadir of the 3 axes of measurements.

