Analysis Populations

All primary analyses will be performed on all tumors with a Galil Medical Cryoablation System and needles as the intent-to-treat evaluable population. A supplemental per-protocol analysis

will be done for the primary endpoint, removing tumors that 1) did not have a complete treatment; and subjects who 2) did not meet the study criteria but were enrolled; or 3) had a deviation with high likelihood of affecting the study outcome (as determined by a review of all occurring deviations).

The intent-to-treat and per-protocol analyses will be compared for level of agreement. It is expected that the two populations will be similar; however, any substantial differences between the two will be analyzed appropriately to elucidate the cause of these differences. Missing data will be imputed for the primary analysis as outlined in section "Handling of Missing Data" section later in the SAP. Additional sensitivity analyses using alternate missing data imputation will be presented.

Efficacy Endpoint Analysis

Efficacy Endpoint

The primary efficacy endpoint for this study is assessment of cryoablation on local tumor control in patients with pulmonary metastatic disease at 12 months post cryoablation.

Analysis Methods

The primary efficacy endpoint for this study is defined as follows: local tumor control in patients with pulmonary metastatic disease at 12 months post cryoablation. Tumor control will be defined by the criteria defined in Section 9.7 of this protocol.

Patients are allowed up to 6 tumors and the primary efficacy endpoint (tumor control) will be calculated on a per tumor level.

The rate of local tumor control at 12-months will be analyzed using a random effects logistic regression model accounting for within subject correlation to account for multiple tumors per subject. The null hypothesis will be tested comparing the lower bound of the Wald 97.5% one-sided confidence interval for the estimated rate of local tumor control to the performance goal of 84.0%. If the lower bound is greater than 84.0%, the null hypothesis will be rejected and the endpoint will be considered met.

Safety Endpoint Analysis

Safety Endpoint

The safety endpoint for this study is to assess the incidence and severity of cryoablation related adverse events.

Analysis Methods

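### Local failure, and so the primary endpoint, is measured against the previous scan in Protocol 8.7 but against the nadir in 8.7.3 and 8.7.4, and the SAP points to a section that does not exist

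*Protocol*

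**What the plan says.** Protocol 5.1 and 10.5.3 make local tumor control of each index tumor at 12 months the primary endpoint, and 5.1 refers to 8.7 for the criteria. Section 8.7 then says: "Local Tumor Control will be defined as the absence of local failure". The endpoint therefore depends on how local failure is determined.

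- **Protocol 8.7, main text.** The sum of the three axes "will be compared to the 1 month baseline for tumor response and the previous follow up interval imaging study for local failure". An earlier sentence in the section adds: "Sequential follow up intervals will be used to determine local failure". Control is also to be "separately assessed for each index tumor according to criteria below".
- **Protocol 8.7.3, stable disease.** The lower limit (less than a 30% decrease) uses the month 1 baseline. The upper limit is a less than 20% "increase of the nadir of the 3 axes of measurements".
- **Protocol 8.7.4, local failure.** A rise of at least 20% in the sum "when compared with the nadir of this 3 axes measurement".
- **Protocol 8.7.1, complete response.** If the investigator believes that the zone "has likely disappeared, the measurement should be recorded as 0mm".
- **SAP, Efficacy Endpoint Analysis.** It gives no definition of its own: "Tumor control will be defined by the criteria defined in Section 9.7 of this protocol". Protocol Section 9 covers device manufacturing and supplies and ends at 9.4, both in the body and in the table of contents.

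**The concern.** One event is given two reference scans. The previous scan and the nadir coincide only while the previous scan is also the smallest so far. Once a zone has shrunk and begun to regrow, or is growing steadily, they part, and the same measurements can be a failure under one sentence and a success under the other.

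Several parties apply this definition: site investigators, the independent imaging panel (Protocol 8.7), the central reviewer (16.2) and the programmer of the SAP analysis. Neither document tells any of them which reference governs. The SAP is where a programmer would expect the question to be settled, and its citation leads nowhere.

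The discrepancy runs in one direction. The previous-scan reading is the more lenient, and what it misses is slow, steady regrowth, which a local-control endpoint ought to detect.

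**Working it through.** **1. The plan's own figures.** Protocol 10.1 gives N = 203 tumors, P0 = 0.84, P1 = 0.91, and rejection if at least 181 tumors are controlled. With X ~ Binomial(203, p):

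- P(X ≥ 181 | p = 0.84) = 0.0239 (stated 0.0239)
- P(X ≥ 181 | p = 0.91) = 0.8501 (stated 0.8501)
- 203 / 0.9 = 225.6, rounded up to 226 (stated 226)

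The sample-size figures reproduce and are not in question.

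**2. Direction of the difference.** At any visit, the nadir is the minimum of the earlier sums and the previous scan is one of those sums, so nadir ≤ previous. If the current sum is ≥ 1.2 × previous, it is also ≥ 1.2 × nadir. Every previous-scan failure is therefore a nadir failure, but not the reverse. With month 1 as reference, the two rules must agree at month 3, because month 1 is the only earlier scan. They can first differ at month 6.

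**3. Largest growth the previous-scan rule can miss by month 12.** The scans are at months 1, 3, 6 and 12, so there are three steps. If each is just under +20%:

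- 1.2³ = 1.728, so just under +73% over a month 1 nadir
- 1.2² = 1.44, so just under +44% if the nadir, or the substitute reference scan, is at month 3

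**4. Hypothetical series.** Start at 60 mm and grow 15% per visit: 60 × 1.15 = 69.0; 69.0 × 1.15 = 79.35; 79.35 × 1.15 = 91.25.

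| Visit | Sum (mm) | vs previous scan | vs nadir (60 mm) |
|---|---|---|---|
| Month 1 | 60 | – | – |
| Month 3 | 69.0 | +15% | +15% |
| Month 6 | 79.35 | +15% | +32% (failure) |
| Month 12 | 91.25 | +15% (control) | +52% (failure) |

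The same happens after initial shrinkage. For sums of 100, 60, 70 and 80 mm, month 12 is 80/70 = +14.3% on the previous scan (control) but 80/60 = +33.3% on the nadir (failure).

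**5. Effect on the test, as illustration.** The documents do not give the share of tumors that the two rules would classify differently. Assume 0.5 to 2 percentage points, which is 0.005 × 203 ≈ 1 to 0.02 × 203 ≈ 4 tumors. Keep the design's independent binomial and its cut-off of 181.

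| Shift (points) | Nadir-based rate 84%, scored by previous scan: P(pass) | Previous-scan rate 91%, scored by nadir: power |
|---|---|---|
| 0 | 0.024 | 0.850 |
| 0.5 | 0.037 (p = 0.845) | 0.783 (p = 0.905) |
| 1 | 0.055 (p = 0.85) | 0.705 (p = 0.90) |
| 2 | 0.113 (p = 0.86) | 0.527 (p = 0.89) |

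**6. The 0 mm case.** The percentage increase is (current − nadir) / nadir. With a nadir of 0 mm this is undefined, and no text says how a zone that reappears is scored.

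**The case against.** The strongest reply is that the protocol contains only one complete rule. Section 8.7.4 is the formal definition, it carries the only growth threshold, 8.7.3 uses the same nadir, and 8.7 sends the reader to the criteria below it. The previous-scan sentence has no threshold and cannot classify a tumor alone; the rival rule appears only if the 20% is carried over to it. On this view it is a stray sentence, and the SAP citation is a clerical slip that Protocol 5.1 lets a reader repair.

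Much of this stands. The nadir is the more natural reading, and the sentence about sequential intervals fits either one, since a nadir is also found from sequential scans. Correcting the citation would not by itself remove the conflict inside 8.7. The 0 mm gap is separate: it arises under either reference, because a previous scan can also be 0 mm.

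It is also fair that the numbers show direction rather than likely impact. The shift is assumed, the binomial ignores within-patient correlation and the SAP's multiple imputation, and the growth limit needs near-threshold growth at every interval. Reader instructions outside these two documents may exist.

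What does not follow is that the text can stay. The 8.7 sentence names a comparator specifically for local failure, it differs from the one in 8.7.4, and nothing says which prevails.

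**Conclusion.** The concern holds. Protocol 8.7 contradicts 8.7.3 and 8.7.4 on the reference scan for local failure, the contradiction lies inside the primary endpoint, and the SAP does not resolve it. The text and the direction of the effect are certain: at a common 20% threshold, the previous-scan reading can never give a lower control rate than the nadir reading.

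The size is not known. The illustrated rise in the chance of passing (from 0.024 to between 0.037 and 0.113) and the illustrated loss of power (from 0.850 to between 0.783 and 0.527) rest on three assumptions: a shift of 0.5 to 2 points, independent tumors, and true rates at exactly 84% or 91%. They do not describe the SAP's random effects logistic model. They do show that a handful of reclassified tumors matters when the margin between the goal and the assumed rate is 7 points. This should be fixed before outcomes are scored.

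**What to change.** - **Protocol 8.7.** Replace the previous-scan wording with the reference already used in 8.7.3 and 8.7.4: an increase of at least 20% over the smallest three-axis sum recorded since the month 1 reference scan, or since the month 3 scan where that serves as reference.
- **SAP, Efficacy Endpoint Analysis.** State the same rule in full and change the citation from Section 9.7 to Protocol 8.7.
- **Imaging panel and central review.** Tell both, in writing, to use this reference.
- **Zero nadir.** Say how a zone that becomes visible again after a 0 mm record is scored. One option is to class it as indeterminate and send it to the independent panel that 8.7 already provides.
- **Optional.** Report the previous-scan version at the same 20% threshold as a sensitivity analysis, so that readers can see how many tumors the choice affects.

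The cost is wording in the protocol, the SAP and the reader instructions. Both versions can be derived from sums already recorded. The reported control rate may be slightly lower than under the previous-scan reading, and reappearing zones with a 0 mm nadir would need a panel decision if that option is taken.

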16.2. Central Imaging Review

Index tumor imaging following cryoablation will be assessed by individual study site investigators. Deidentified images will be assessed by a qualified third party central reviewer for assessment and

adjudication. The image review will be conducted by physicians who are board certified in radiology with experience in tumor assessment following ablation.

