Demographics, disease status, imaging data, lung function, and protocol deviations will be summarized using descriptive statistics. These measures include but may not be limited to:

Demographics

- Age at the date of consent
- Sex
- Race and ethnicity (Per French regulations, race and ethnicity will not be collected at any study site in France.)
- Height, weight, and BMI
- Comorbidities
- Smoking history
- Concomitant medications

Disease status

- Primary cancer diagnosis
- Prior treatment(s) for lung metastases
- Lung or other metastatic disease
- Baseline laboratory data

Index Tumor(s)

- Histology of primary tumor
- Proof of metastases
- Location of the index tumor(s) in the lung(s)
- Size of the index tumor(s)
- Number of index tumors
- Number of new tumors

Procedure/Discharge

- Number of tumors treated with cryoablation
- Index tumor size measurement:
 - 3 axes of measurements (cm) and
- Number and type of cryoablation needles used
- Freeze and thaw times, per cycle
- Number and type of intra-operative complication(s)
- Severity of complication(s)
- Requirement for hospital admittance/stay
- Requirement for surgical intervention(s)

All protocol deviations

Study Completion/Withdrawals

Subject Disposition

Subject disposition will be presented as:

- Number of subjects enrolled

- Number of subjects completing each follow-up visit
- Number of subjects withdrawn or lost to follow-up
- Number of subject deaths
- Number of subjects evaluable for ITT and PP analyses

Randomization and Blinding

As this is a single arm study, no randomization or blinding will be performed. To minimize selection bias within the enrolled patient population, participation in the study is to be offered to all eligible patients on a consecutive basis as they present to the physician at the site.

Handling of Missing Data

Missing data will be prospectively minimized through training of the participating investigator and site staff, and through appropriate clinical trial management. Every effort will be made to collect all data points in the study. All patient data that is available on patients who drop out during the course of the study will be included where possible. Sensitivity analyses will be conducted to determine the effect of missing data on the primary efficacy endpoint.

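### The plan does not settle whether the site read or the independent central read is the primary endpoint value: Section 8.7 conflicts within itself and with Section 16.2, and the SAP names no reader

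*Protocol*

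**What the plan says.** **Protocol 8.7, Response Determination.** Each ablation zone measurement, together with the patient's overall clinical evaluation, "will be evaluated by an independent imaging panel to assess the final response determinations". The following sentence begins "This final review can be used in the analysis in the event of" and ends by referring to indeterminate measurements. It is the only sentence in 8.7 that says how the panel's result enters the analysis. The term indeterminate is not defined.

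**Protocol 16.2, Central Imaging Review.** "Index tumor imaging following cryoablation will be assessed by individual study site investigators". The section continues: "Deidentified images will be assessed by a qualified third party central reviewer for assessment and" adjudication. It does not restrict this to indeterminate cases and gives no rule for disagreement.

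**Protocol 8.7.1, Complete Response.** "If it is the opinion of the investigator that the tumor/ablation zone has likely disappeared, the measurement should be recorded as 0mm". Investigator judgement therefore enters the recorded measurements.

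**Protocol 10.5.3 and the SAP's Efficacy Endpoint Analysis.** Both define the per-tumour 12-month rate and name no reader. For the criteria the SAP says: "Tumor control will be defined by the criteria defined in Section 9.7 of this protocol". Section 9 of the protocol covers device supply and ends at 9.4; the response criteria are in 8.7. The SAP's listed sensitivity analyses concern missing data only, and none compares site with central reads. On masking it says: "As this is a single arm study, no randomization or blinding will be performed".

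**The concern.** The trial has one arm and tests per-tumour local control against a fixed goal of 84%. With no control arm read by the same people, a systematic shift in how images are called does not cancel; it moves the observed rate relative to the goal. Failure is a numeric rule (at least a 20% rise over the nadir in the sum of three axes), but someone has to draw those axes around an evolving ablation zone and decide when it has gone.

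Two sets of reads will exist for the same zones, one from the treating sites and one from an independent body. If the plan does not say which is analysed, two analysts could follow it faithfully and reach different answers, and the choice could be made with both results in view.

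**Working it through.** **Step 1: set the texts side by side.**

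- 8.7, first sentence on the panel: every zone is reviewed, and the output is the final determination. This points to the panel.
- 8.7, second sentence: the review may be used when measurements are indeterminate. Naming one permissive trigger implies that determinate measurements stand without it. Taken with 8.7.1 and the first sentence of 16.2, those measurements are most naturally the site's.
- 16.2, second sentence: the central reviewer assesses and adjudicates without restriction. This points back to the central read.
- 10.5.3 and the SAP: silent.

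The texts give two tenable answers and no rule to choose between them. Three further gaps follow:

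- It is not stated whether the panel in 8.7 and the central reviewer in 16.2 are the same body. The first sees the clinical evaluation; the second is described only as assessing deidentified images.
- The SAP multiply imputes missing 12-month evaluations. Nothing says whether an indeterminate site read counts as missing (imputed) or is replaced by the panel's read.
- The reader matters at every visit, not just month 12. Failure is judged against the nadir, and the SAP carries a 6-month failure forward to 12 months.

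**Step 2: reproduce the planned design (Protocol 10.1; SAP, Sample Size Justification).** Inputs: N = 203, reject if at least 181 are controlled, p0 = 0.84, p1 = 0.91.

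- P(X ≥ 181 | 203, 0.84) = 0.0239, as stated. A cutoff of 180 would give 0.0384, so 181 is correct.
- P(X ≥ 181 | 203, 0.91) = 0.8501, as stated.
- 203 / 0.90 = 225.6, rounded up to 226, as stated.

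**Step 3: illustrate sensitivity to the reader.** The documents give no reader error rates, so these are assumptions. Let t be the true control rate, f the share of true failures read as controlled, and g the share of true controls read as failures. The apparent rate is

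p = t(1 − g) + (1 − t)f.

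At t = 0.84, with tumours treated as independent:

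| f | g | Apparent rate p | P(at least 181 of 203) |
|---|---|---|---|
| 0 | 0 | 0.8400 | 2.4% |
| 5% | 0 | 0.84 + 0.16 × 0.05 = 0.8480 | 4.7% |
| 10% | 0 | 0.84 + 0.16 × 0.10 = 0.8560 | 8.6% |
| 20% | 0 | 0.84 + 0.16 × 0.20 = 0.8720 | 23.6% |
| 10% | 2% | 0.8232 + 0.016 = 0.8392 | 2.2% |
| 20% | 2% | 0.8232 + 0.032 = 0.8552 | 8.1% |

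The two kinds of error cancel when g = f(1 − t)/t: for f = 10%, 0.016/0.84 = 1.9%; for f = 20%, 0.032/0.84 = 3.8%.

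Errors in the other direction cost power. At t = 0.91 and f = 0, g = 1% gives p = 0.9009 and power 71.9%; g = 2% gives p = 0.8918 and power 56.0%, against 85.0% with no error.

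**The case against.** A reader might infer that the treating sites' reads decide the primary endpoint and that the panel is confined to indeterminate cases. The documents do not support that as a statement of fact. The word *only* does not appear in 8.7, the same paragraph calls the panel's output final, and 16.2 gives the central reviewer an unrestricted adjudicating role. The indeterminate sentence could also be contrasting pure measurement with a review that adds clinical information, rather than site with panel. This objection stands, and it limits the point to an unresolved contradiction.

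Section 10.5.5 might be cited in support, since local disease progression "will be determined locally by evidence of local tumor failure". That text belongs to the other data assessments, not the primary endpoint, and *locally* may mean at the tumour rather than by the site. It carries no weight here.

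A reader might also take 8.6% or 23.6% as the trial's real false positive rate. They are not. They assume errors in one direction only, independent tumours and the sample-size binomial rule. The SAP's primary test is a Wald bound from a random-effects logistic model after multiple imputation. The numeric failure rule limits reader discretion, and modest opposite errors can cancel the effect. Nothing in the documents shows that sites would read leniently, or that anyone has chosen a read after seeing results.

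Finally, central readers also know that every patient was treated. The gain from using them is independence from the treating team, not blinding to treatment.

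None of this supplies the missing rule. If both readings are fair, the plan contradicts itself on where its primary endpoint comes from.

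**Conclusion.** The point holds as a contradiction to be resolved. Section 8.7 is inconsistent within itself and with 16.2, and neither 10.5.3 nor the SAP says which read is the primary endpoint value when site and central reads disagree. The natural reading of 8.7 leaves determinate site reads standing; the alternative makes the panel final. The source is therefore open to choice after the results are known.

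The direction and size of any reader bias cannot be found from the documents. The calculation shows only that the conclusion is sensitive to the choice. Under the assumed error rates tabulated above, the false positive rate at true control of 84% lies between 2.2% and 23.6%, against 2.4% with error-free reading. At a true rate of 91%, misreading 2% of controlled tumours as failures, with no opposite errors, would by itself reduce power from 85.0% to 56.0%. In a single-arm comparison with a fixed goal, that is enough to justify settling the reader in advance. An independent read of the same zones is already planned and is the better primary source.

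**What to change.** State in Protocol 8.7, Protocol 16.2 and the SAP that the independent central read is the primary endpoint value for every index tumour at every visit. In the same change:

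- Remove the sentence about indeterminate measurements, or reconcile it with that rule. If the term stays, define it and say whether such a read is treated as missing for the multiple imputation.
- Say whether the panel in 8.7 and the central reviewer in 16.2 are the same body, how adjudication works, and whether the central readers see the clinical evaluation and the site result.
- Report the site read as a pre-specified sensitivity analysis of the primary endpoint, with site-central agreement.
- Correct the SAP's reference to Section 9.7 so that it points to 8.7.

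The change needs no extra patients or imaging and leaves the target of 226 tumours as it is. The cost is document wording, and the primary analysis has to wait for the central reads to be complete.
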